APPENDIX A: TOTAL BILIRUBIN TABLE FOR TERM AND PRETERM NEONATES

PARAMETER	GRADE 1 MILD	GRADE 2 MODERATE	GRADE 3 SEVERE	GRADE 4 POTENTIALLY LIFE- THREATENING
Total Bilirubin¹⁹, High (mg/dL; μmol/L)²⁰				
Term Neonate²¹				
<24 hours of age	4 to <7 68.4 to <119.7	7 to <10 119.7 to <171	10 to <17 171 to <290.7	≥17 ≥290.7
24 to <48 hours of age	5 to <8 85.5 to <136.8	8 to <12 136.8 to <205.2	12 to <19 205.2 to <324.9	≥19 ≥324.9
48 to <72 hours of age	8.5 to <13 145.35 to <222.3	13 to <15 222.3 to <256.5	15 to <22 256.5 to <376.2	≥22 ≥376.2
72 hours to <7 days of age	11 to <16 188.1 to <273.6	16 to <18 273.6 to <307.8	18 to <24 307.8 to <410.4	≥24 ≥410.4
7 to 28 days of age (breastfeeding)	5 to <10 85.5 to <171	10 to <20 171 to <342	20 to <25 342 to <427.5	≥25 ≥427.5
7 to 28 days of age (not breastfeeding)	1.1 to <1.6 x ULN	1.6 to <2.6 x ULN	2.6 to <5.0 x ULN	≥5.0 x ULN
Preterm Neonate²⁰				
35 to <37 weeks gestational age	Same as for Total Bilirubin, High, Term Neonate (based on days of age).	Same as for Total Bilirubin, High, Term Neonate (based on days of age).	Same as for Total Bilirubin, High, Term Neonate (based on days of age).	Same as for Total Bilirubin, High, Term Neonate (based on days of age).
32 to <35 weeks gestational age and <7 days of age	NA	NA	10 to <14 171 to <239.4	≥14 ≥239.4
28 to <32 weeks gestational age and <7 days of age	NA	NA	6 to <10 102.6 to <171	≥10 ≥171
<28 weeks gestational age and <7 days of age	NA	NA	5 to <8 85.5 to <136.8	≥8 ≥136.8
7 to 28 days of age (breastfeeding)	5 to <10 85.5 to <171	10 to <20 171 to <342	20 to <25 342 to <427.5	≥25 ≥427.5
7 to 28 days of age (not breastfeeding)	1.1 to <1.6 x ULN	1.6 to <2.6 x ULN	2.6 to <5.0 x ULN	≥5.0 x ULN

¹⁹ Severity grading for total bilirubin in neonates is complex because of rapidly changing total bilirubin normal ranges in the first week of life followed by the benign phenomenon of breast milk jaundice after the first week of life. Severity grading in this appendix corresponds approximately to cut-offs for indications for phototherapy at grade 3 and for exchange transfusion at grade 4.

²⁰ A laboratory value of 1 mg/dL is equivalent to 17.1 μmol/L.

²¹ Definitions: Term is defined as ≥37 weeks gestational age; near-term, as ≥35 weeks gestational age; preterm, as <35 weeks gestational age; and neonate, as 0 to 28 days of age.

AV = atrioventricular; BPAP = bilevel positive airway pressure; CPAB = continuous positive airway pressure; INR = international standardized ratio; LLN = lower limit of normal; NA = not applicable; PT = prothrombin time; PTT = partial thromboplastin time; QTc = corrected QT; SGPT = serum glutamic pyruvic transaminase; WHO = World Health Organisation

Attachment 2: Cardiovascular Safety – Abnormalities**ECG**

All important abnormalities from the ECG readings will be listed.

Abnormality Code	ECG parameter			
	HR	PR	QRS	QT _{corrected}
Abnormalities on actual values				
Abnormally low	≤ 45 bpm	NAP	≤ 50 ms	-
Abnormally high	≥ 120 bpm	≥ 210 ms	≥ 120 ms	-
[450 ms, 480 ms]	-	-	-	450 ms < QTc ≤ 480 ms
[480 ms, 500 ms]	-	-	-	480 ms < QTc ≤ 500 ms
More than 500 ms	-	-	-	QTc > 500 ms
Abnormalities on changes from baseline				
[30; 60] ms	-	-	-	[30; 60] ms
> 60 ms	-	-	-	> 60 ms

For absolute QTc parameters the categories are defined based on the ICH E14 Guidance ^a

Vital Signs^b

The following abnormalities will be defined for vital signs:

Abnormality Code	Vital Signs parameter		
	Pulse	DBP	SBP
Abnormalities on actual values			
Abnormally low	≤ 45 bpm ≤ 50 bpm	≤ 50 mmHg	≤ 90 mmHg
Grade 1 or mild	-	> 90 mmHg - < 100 mmHg	> 140 mmHg - < 160 mmHg
Grade 2 or moderate	-	≥ 100 mmHg - < 110 mmHg	≥ 160 mmHg - < 180 mmHg
Grade 3 or severe	-	≥ 110 mmHg	≥ 180 mmHg
Abnormally high	≥ 120 bpm	-	-

^a The clinical evaluation of QT/QTc interval prolongation and proarrhythmic potential for non-antiarrhythmic drugs. CHMP/ICH/2/04, May 2005.

^b The classification of AEs related to hypotension and hypertension will be done according to the DAIDS grading scale (see also Attachment 1).

INVESTIGATOR AGREEMENT

I have read this protocol and agree that it contains all necessary details for carrying out this study. I will conduct the study as outlined herein and will complete the study within the time designated.

I will provide copies of the protocol and all pertinent information to all individuals responsible to me who assist in the conduct of this study. I will discuss this material with them to ensure that they are fully informed regarding the study drug, the conduct of the study, and the obligations of confidentiality.

Coordinating Investigator (where required):

Name (typed or printed): _____

Institution and Address: _____

Signature: _____ Date: _____
(Day Month Year)

Principal (Site) Investigator:

Name (typed or printed): _____

Institution and Address: _____

Telephone Number: _____

Signature: _____ Date: _____
(Day Month Year)

Sponsor's Responsible Medical Officer:

Name (typed or printed): _____

Institution: _____ Janssen Pharmaceutical K.K.

Signature: _____ electronic signature appended at the end of the protocol Date: _____
(Day Month Year)

ADR	Adverse Drug Reaction
ALT	alanine aminotransferase
AUC_{last}	area under the plasma concentration-time curve from time zero to time the last quantifiable time, calculated by linear trapezoidal summation
AUC_{∞}	area under the plasma concentration-time curve from time zero to infinite time
BMI	body mass index
BQL	Below quantifiable limit
C_{last}	concentration at last quantifiable time point
C_{max}	maximum plasma concentration
COBI	Cobicistat
CV	coefficient of variation
DRV	Darunavir
ECG	electrocardiogram
FDC	Fixed-dose combination
HIV	human immunodeficiency virus
ICF	informed consent form
MedDRA	Medical Dictionary for Regulatory Activities
PK	pharmacokinetic
PT	preferred term
RBC	red blood cell
SAE	Serious Adverse Event
SAP	Statistical Analysis Plan
SD	standard deviation
SDTM	Study Data Tabulation Model
SOC	system organ class
TEAE	treatment-emergent adverse event
$t_{1/2,term}$	terminal elimination half-life
t_{max}	time to reach the maximum plasma concentration
WBC	white blood cell
λ_z	elimination rate constant associated with the terminal phase

1. INTRODUCTION

This statistical analysis plan (SAP) contains definitions of analysis sets, derived variables, and statistical methods for all planned analyses of Protocol TMC114FD1HTX4002.

1.1. Trial Objectives

Primary Objective

The primary objective is to evaluate the PK of Darunavir (DRV) and Cobicistat (COBI) after a single oral administration of Prezcobix DRV and COBI fixed-dose combination tablet, to healthy Japanese adult subjects.

Secondary Objectives

The secondary objective is to evaluate the safety after a single oral administration of Prezcobix to healthy Japanese adult subjects.

1.2. Trial Design

This is a single center open-label, single oral dose study in healthy Japanese adult subjects. The study consists of 3 phases; a screening phase from Day -21 to Day -2, an in-patient phase from Day -1 to Day 4 (dosing day is Day 1), and a follow-up assessment phase scheduled 7 to 10 days after the intake of the study drug or at the time of early withdrawal.

1.3. Statistical Hypotheses for Trial Objectives

No formal statistical hypothesis testing is planned for this study. This study is designed to collect PK data in Japanese subjects after a single oral administration of Prezcobix under a fed condition.

1.4. Sample Size Justification

Eight subjects will be enrolled in the study to ensure that at least 6 subjects complete the study assessments up to Day 4. Based on a previous study, TMC114IFD1003, the maximum observed value of between subject coefficient of variation (CV) for C_{max} , AUC_{last} and AUC_{∞} for DRV and COBI after intake of DRV and COBI as a Fixed-dose combination (FDC) tablet under fed conditions were 35% for DRV and 44% for COBI in healthy non Japanese adult subjects. Using an estimate of approximately 40% for between subject CV and a sample size of 6 subjects, the true mean C_{max} , AUC_{last} and AUC_{∞} for each component of DRV and COBI are estimated to be within 73% to 137% of the observed geometric means with 90% confidence.

1.5. Randomization and Blinding

As this is an open study, blinding procedures are not applicable. No randomization is planned in this study. All the subjects will be assigned to the same treatment.

2. GENERAL ANALYSIS DEFINITIONS

2.1. Visit Windows

The evaluations are described in “Time and Events Schedule” of the protocol and the allowance are described below.

Analysis time point		Allowance	Physical Examination	Vital Signs a), b)	12-lead ECG ^{a)}	Clinical Labs ^{c)}
Screening		Day -21 to Day -2	X	X	X	X
Day -1		Within Day-1	X	X	X	X
Day 1	Predose	Within Day1 and before intake of Prezcobix	X	X	X	
	3 hr	Within Day1 and +/- 30 min.		X	X	
Day 2		Within Day 2	X	X	X	X
Day 4		Within Day 4	X	X	X	X
End-of-Study (Day 7 -10)		Within the day Day 7 -10	X	X	X	X

a) When blood samples are to be collected and 12-lead ECG and/or vital signs are to be checked at the same time point, blood samples will be collected after completion of other evaluations.

b) Vital signs include respiration rate, supine blood pressure, pulse and temperature (axillary) after more than 5 minutes rest.

c) Clinical labs include hematology, biochemistry and urinalysis. Subjects will fast for at least 10 hours prior to the blood sampling for clinical labs.

Pharmacokinetics

Analysis time point		Allowance	Pharmacokinetics
Day 1	Predose	Before intake of Prezcobix	X ^{a)}
	0 hr		
	0.5 hr	0.4 hr to 0.6 hr	X
	1 hr	0.8 hr to 1.2 hr	X
	1.5 hr	1.25 hr to <1.75 hr	X
	2 hr	1.75 hr to <2.25 hr	X
	2.5 hr	2.25 hr to <2.75 hr	X
	3 hr	2.75 hr to 3.25 hr	X ^{a)}
	4 hr	3.5 hr to <4.5 hr	X
	5 hr	4.5 hr to <5.5 hr	X
	6 hr	5.5 hr to 6.5 hr	X
	9 hr	8.0 hr to <10.0 hr	X
	12 hr	10.0 hr to <14.0 hr	X
	16 hr	14.0 hr to <18.0 hr	X
	20 hr	18.0 hr to <22.0 hr	X
Day 2	24 hr	22.0 hr to 26.0 hr	X ^{a)}
	36 hr	30.0 hr to <42.0 hr	X
Day 3	48 hr	42.0 hr to <54.0 hr	X
	60 hr	54.0 hr to <66.0 hr	X
Day 4	72 hr	66.0 hr to 78.0 hr	X ^{a)}
End-of-Study (Day 7-10)/ Early Withdrawal			X ^{a) b)}

a) When blood samples are to be collected and 12-lead ECG and/or vital signs are to be checked at the same time point, blood samples will be collected after completion of other evaluations.

b) At the end of study or early withdrawal, sample PK will be performed for early withdrawal visit only.

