This is a single center open-label, single oral dose study in healthy Japanese adult subjects. The study consists of 3 phases; a screening phase from Day -21 to Day -2, an in-patient phase from Day -1 to Day 4 (dosing day is Day 1), and a follow-up assessment phase scheduled 7 to 10 days after the intake of the study drug or at the time of early withdrawal.

SUBJECT POPULATION

Eight subjects will be enrolled to ensure that at least 6 subjects complete the study up to Day 4. If more than 2 subjects withdraw from the study before completion up to Day 4 for reasons other than safety, additional subjects will be enrolled to ensure that at least 6 subjects complete the study up to Day 4.

Main Criteria for Inclusion

Healthy Japanese men and women between 20 and 55 years of age, inclusive; body mass index (BMI) between 18.0 and 30.0 kg/m², inclusive; and body weight not less than 50 kg.

DOSAGE AND ADMINISTRATION

One Prezcobix tablet will be taken in the morning on Day 1. The study drug will be taken orally with 240 mL of noncarbonated water within 30 minutes after start of the standardized breakfast, and the breakfast should be fully ingested within 30 minutes. The study drug must be swallowed whole, not chewed, divided, dissolved or crushed.

PHARMACOKINETIC EVALUATIONS

Venous blood will be collected for the determination of plasma concentrations for each component of DRV/COBI at the following time points;

- Predose, 0.5, 1, 1.5, 2, 2.5, 3, 4, 5, 6, 9, 12, 16, 20, 24, 36, 48, 60, 72 hours postdose and early withdrawal visit

Based on the individual plasma concentration-time data, using the actual sampling times, the following PK parameters will be estimated by noncompartmental analysis. Additional PK parameters may be estimated as well.

PK parameters for DRV and COBI: C_{\max} , C_{last} , t_{\max} , AUC_{last} , AUC_{∞} , λ_z , $t_{1/2,\text{term}}$

SAFETY EVALUATIONS

Safety will be evaluated throughout the study. Following evaluations will be performed according to the TIME AND EVENTS SCHEDULE.

- Adverse Events (AEs)
- Clinical Laboratory Tests
 - - Hematology Panel
 - - Biochemistry Panel
 - - Urinalysis
- 12-lead Electrocardiogram (ECG)
- Vital Signs (blood pressure, pulse, temperature [axillary], respiration rate)
- Physical Examination

Any clinically significant abnormalities persisting at the end of the study will be followed by the investigator until resolution or until reaching a clinically stable endpoint.

STATISTICAL METHODS

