Sample Size Determination

Eight subjects will be enrolled in the study to ensure that at least 6 subjects complete the study assessments up to Day 4. Based on a previous study, TMC114FD1003, the maximum observed value of between subject coefficient of variation (CV) for C_{\max} , AUC_{last} and AUC_{∞} for DRV and COBI after intake of DRV/COBI as an FDC tablet under fed conditions were 35% for DRV and 44% for COBI in healthy nonJapanese adult subjects. Using an estimate of approximately 40% for between subject CV and a

sample size of 6 subjects, the true mean C_{\max} , AUC_{last} and AUC_{∞} for each component of DRV/COBI are estimated to be within 73% to 137% of the observed geometric means with 90% confidence.

Pharmacokinetics

All subjects receiving the study drug and having at least one plasma concentration data after administration will be included in the pharmacokinetic analysis. Plasma concentration data will be tabulated for each component of DRV/COBI. Individual and mean concentration time profiles for each analyte will be visually presented on a linear and logarithmic scale. PK parameters for each analyte will be calculated using data of all the subjects whose concentration-time profiles allow for accurate calculation of PK parameters. The descriptive statistics (eg, number of collected data, mean, standard deviation, median, minimum, maximum, CV and geometric means) of plasma concentrations of each analyte at each time point will be reported. Individual and descriptive statistics of PK parameters of each analyte will be tabulated.

Safety

All subjects who received the study drug will be included in the safety and tolerability analysis. Baseline for all laboratory evaluations, vital signs and ECG will be defined as the last evaluation done before the study drug administration. Safety will be evaluated by examining frequency, severity and type of AEs, and changes in clinical laboratory test values (hematology, biochemistry and urinalysis), physical examination results, vital signs and ECG measurements. Safety data will be summarized using descriptive statistics and frequency tables.

TIME AND EVENTS SCHEDULE

Phase	Screening	In-patient period														End-of-Study							
Study day	Days -21 to -2	Day -1	Day 1												Day 2	Day 3	Day 4	End of Study (Day 7 – 10) or Early Withdrawal					
Time			0 h	0.5 h	1 h	1.5 h	2 h	2.5 h	3 h	4 h	5 h	6 h	9 h	12 h	16 h	20 h	24 h	36 h	48 h	60 h	72 h		
Informed consent (ICF)	X																						

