3. STUDY DESIGN AND RATIONALE

3.1. Overview of Study Design

This is a single center open-label, single oral dose study in healthy Japanese adult subjects. Eight subjects will be enrolled to ensure that at least 6 subjects complete the study up to Day 4. The study consists of 3 phases; a screening phase from Day -21 to Day -2, an in-patient period-phase from Day -1 to Day 4 (dosing day is Day 1), and an End of Study phase with a visit scheduled 7 to 10 days after the intake of study drug or at the time of early withdrawal.

As depicted in [Figure 1](#), eight subjects who satisfy all inclusion criteria and do not meet any exclusion criteria will receive Prezcobix at Day 1. Subjects who met the selection criteria at screening will be admitted to the investigational institute on the day before administration (Day -1). All enrolled subjects will receive a single oral dose of one Prezcobix tablet on Day 1 (there is no Day 0) within 30 minutes after start of the standardized breakfast (see [Figure 1](#)), and the breakfast should be fully ingested within 30 minutes. All subjects will remain in the investigational institute for the entire duration of the in-patient phase. Subjects will be discharged on Day 4 after the completion of all required assessments. Subjects will visit the investigational institute on the days as scheduled until the last follow-up assessment on Day 7 - Day 10. Serial blood samples for the determination of plasma concentrations for each component of Prezcobix will be collected over a period of 72 hours. Details on the timing of the dose and the PK and safety assessments are given in the [TIME AND EVENTS SCHEDULE](#).

Figure 1: Schedule Overview of the Study

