2.6. Other Methodological Notes

Calculation for study day:

- Post-treatment study day: [The date of a respective event] – [The date of Prezcobix dose] +1
- Pre-treatment study day: [The date of a respective event during pre-dosing time] – [The date of first Prezcobix dose]

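### Do the two wordings of the follow-up visit, and the missing Early Withdrawal label in SAP 2.1, leave safety values out of the tables?

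*SAP*

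**What the plan says.** The follow-up visit is worded in two ways.

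- **Days after intake.** The protocol synopsis has "a follow-up assessment phase scheduled 7 to 10 days after the intake of the study drug or at the time of early withdrawal". SAP 1.2 repeats the same timing ("a follow-up assessment phase scheduled 7 to 10 days after the intake of the study drug"), and protocol 3.1 has "a visit scheduled 7 to 10 days after the intake of study drug".
- **Study-day numbers.** A later sentence of protocol 3.1 keeps subjects returning "until the last follow-up assessment on Day 7 - Day 10". The column of the Time and Events Schedule is headed "End of Study (Day 7 – 10) or Early Withdrawal". The SAP 2.1 safety table gives the allowance "Within the day Day 7 -10".

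Dosing is on Day 1 and protocol 3.1 states that there is no Day 0. For post-treatment days, SAP 2.6 takes the event date and subtracts "The date of Prezcobix dose] +1".

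Protocol 9.1.4 calls for physical examination, laboratory tests, vital signs and ECG at the end of study or at early withdrawal. The SAP 2.1 pharmacokinetics table carries the joint label "End-of-Study (Day 7-10)/ Early Withdrawal"; the safety table labels its last row as end of study only. The by-visit and shift tables for laboratory tests, vital signs and physical examination (SAP 6.2 and 6.3), and the vital-sign table of values beyond clinically important limits, are to use the time points of SAP 2.1. SAP 6.4 summarises the ECG interpretation by scheduled time point, and ECG has its own column in the SAP 2.1 table.

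**The concern.** Two gaps seem to open. First, a visit 10 days after intake complies with SAP 1.2 but falls outside the window in SAP 2.1 of the same document. Second, a subject who withdraws early is assessed, and those values count as on-treatment because the SAP's definition runs to the withdrawal date. On several dates, however, they match no row in the safety table.

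Safety is the secondary objective and only 8 subjects are enrolled, so one subject is a visible share of any table. If one analyst dropped the unmatched values and another placed them in the end-of-study row, their shift tables and beyond-limits table could differ although the data were the same.

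**Working it through.** **Step 1: the day arithmetic.** Study day = days after intake + 1 (SAP 2.6). As a check on the convention, 24 h is 1 day after intake, giving 1 + 1 = Day 2, and 72 h is 3 days after, giving 3 + 1 = Day 4. Both agree with the Schedule. For follow-up:

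- 7 days after intake: 7 + 1 = Day 8
- 10 days after intake: 10 + 1 = Day 11

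| Wording | Study days |
|---|---|
| 7 to 10 days after intake | 8, 9, 10, 11 |
| Day 7 to Day 10 | 7, 8, 9, 10 |
| Meet both | 8, 9, 10 |
| Only in the first | 11 |
| Only in the second | 7 |

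Together the wordings allow five days, and three of them meet both. Only Day 11 is without a row in the SAP 2.1 safety table.

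**Step 2: withdrawal dates without a row, Day 1 after dosing to Day 6.**

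| Assessment | Post-dose rows in SAP 2.1 before Day 7 | Days with no row |
|---|---|---|
| Laboratory tests, physical examination | Day 2, Day 4 | 1, 3, 5, 6 |
| Vital signs, ECG | Day 1 at 3 h ± 30 min, Day 2, Day 4 | 3, 5, 6, and Day 1 outside 2.5 to 3.5 h |

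These are counts of calendar days, not probabilities. The documents give no rate of withdrawal on these days and no rate of Day 11 visits. Day 1 is also a weak case for laboratory tests. SAP 2.1 asks for a fast of at least 10 hours and dosing accompanies breakfast, so a compliant sample after dosing could come only late that day.

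**Step 3: what the documents offer to fill the gap.**

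- *Follow-up day.* For the timing of assessments, protocol 3.1 sends the reader to the Time and Events Schedule. That Schedule, the day-numbered sentence in protocol 3.1 and SAP 2.1 all say Day 7 to 10. The days-after-intake form appears only in overview sentences. A site that schedules from the Schedule does not book Day 11.
- *Early withdrawal.* SAP 2.1 opens by taking its evaluations from the Schedule, which has a single joint column for end of study and early withdrawal. Protocol 9.1.4 lists one set of assessments for both, and the pharmacokinetics table keeps the joint label. The safety row is most naturally read as that column with a shortened label.
- *Exclusion.* The only rule that removes data for being outside a window is in SAP 7.1, and it covers plasma concentrations. There is none for safety values.

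**Step 4: what stays intact under the most literal reading.** The laboratory, vital-sign, physical-examination and ECG listings keep all results. There are separate listings of out-of-range and markedly abnormal laboratory and vital-sign values. Individual laboratory and vital-sign plots use every observed time point. Under protocol 9.5, clinically relevant changes are recorded as adverse events, and the adverse event tables do not use SAP 2.1.

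**Step 5: size of a possible discrepancy.** Suppose the only subject with a vital sign beyond limits had that value on an unmatched date. With all 8 treated subjects as denominator, the table would show 0 of 8 instead of 1 of 8 (1/8 = 12.5%). If the denominator were subjects with a value at that time point, and this subject alone had none, it would show 0 of 7. The SAP does not say which denominator applies, so 12.5% is an illustration and not a figure from the plan.

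**The case for a change.** The best case for a change is that the mapping is inferred and not written. No SAP sentence assigns withdrawal values to the end-of-study row, and its Day 7 to 10 allowance literally excludes earlier dates. The case is foreseeable too. Eight subjects are enrolled so that at least 6 complete Day 4, so the design allows for 8 − 6 = 2 losses. Protocol 10.2 also withdraws subjects who vomit within 6 hours of dosing, which can lead to an assessment on Day 1. The shared column says nothing about Day 11. A correction would cost one label and a few words.

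The textual part of this stands: the wordings differ by a day, the label is missing, and ECG shares the ambiguity with the other assessments. What does not follow is that values would be lost or a result made unsound. An analyst who meets a withdrawal value has a joint column to follow, an on-treatment definition that includes the value, and no instruction to discard it. A Day 11 visit would depart from the Schedule; its results would still be listed and, for laboratory tests and vital signs, plotted. That a correction is cheap does not show that one is needed.

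**Conclusion.** No change to the plan follows. The follow-up wording is a one-day clerical slip between overview sentences and the operative schedule. The missing Early Withdrawal label is a gap that analysts can fill sensibly from the Schedule's joint column.

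The effect is confined to the by-time-point and shift summaries, the mean plots and the vital-sign beyond-limits table, and only if a subject is assessed on an unmatched date. It would then typically amount to one subject in a cell. The study is descriptive, has no hypothesis test, and its primary objective is pharmacokinetic. No safety conclusion would rest on such a cell when the listings and adverse event records are complete.

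This rests on two assumptions: that follow-up visits are booked from the Time and Events Schedule, and that analysts read the end-of-study safety row as the Schedule's joint column. The documents support both readings but state neither outright.
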